---

## 1 Acronyms

American College of Obstetricians and Gynecologists	ACOG	Institutional Review Board	IRB
Anti-Mullerian Hormone	AMH	Intramuscular	IM
Aromatase Inhibitors	AI	Intrauterine Insemination	IUI
Assisted Reproductive Technologies	ART	Investigational New Drug	IND
Catechol-O-methyl transferase	COMT	Luteinizing Hormone	LH
Centers for Disease Control	CDC	Methylenetetrahydrofolate reductase	MTHFR
Clinical Report Form	CRF	National Institute of Child Health and Human	NICHD
Clomiphene Citrate	CC	Office for Human Research Protections	OHRP
Data Coordination Center	DCC	Ovarian Hyperstimulation Syndrome	OHSS
Data and Safety and Monitoring	DSMB	Ovarian Stimulation	OS
Epigallocatechin gallate	EGCG	Principal Investigator	PI
Estradiol	E2	Progesterone	P4
Estrogen	E	Protected Health Information	PHI
Estrogen Receptor	ER	Quality of Life	QOL
Follicle Stimulating Hormone	FSH	Serious Adverse Event	SAE
Health Insurance Portability and Accountability Act	HIPAA	Thyroid-Stimulating Hormone	TSH
Health Related Quality of Life	HRQL	Total and Free Testosterone	T, FT
Human Chorionic Gonadotropin	hCG	Ultrasound	U/S
Human Investigation Committee	HIC	World Health Organization	WHO
Identification	ID		

## 2 Study Synopsis

### 2.1 Objectives

The objective of this study is to conduct a randomized clinical trial to determine the pharmacokinetics and hepatic safety of epigallocatechin gallate (EGCG).

MTHFR represents the most studied enzyme in the folate pathway with strong evidence that polymorphisms decrease enzyme activity. Because of the potential effect of EGCG on folate metabolism possibly leading to folate depletion, MTHFR represents a clinically relevant target. We are planning to stratify subjects by wild type MTHFR, MTHFR (C677T), and MTHFR (A1298C). The prevalence of MTHFR mutations can range from 30 to 40% in the American population for C677T and ~50% for A1298C. We will evaluate if green tea catechins may have modulating properties that may increase the risk of folic acid depletion in women expressing known MTHFR polymorphisms. In this protocol we will evaluate if polymorphisms related to folate metabolism increase the risk for folate depletion in women receiving green tea extract.

### 2.2 Patient Population

The population will consist of 36 women ages  $\geq 18$  to  $\leq 40$  years (at time of consent). Eighteen women will have intramural and/or subserosal fibroids and 18 women will be without intramural fibroids and/or subserosal fibroids. Participants will be recruited over approximately a 6-month period from the FRIEND Collaborative clinical sites (Johns Hopkins University, University of Illinois at Chicago, University of Chicago and Yale University).

### 2.3 Study Design

Randomization will be stratified by age (age 18-29, 30-40) and presence of fibroids. The randomization scheme will be coordinated through the data coordination center (DCC).

### 2.4 Treatment

The 36 women will be randomized to one of the following groups:

1. EGCG daily alone.
2. EGCG daily with clomiphene citrate 100mg for 5 days.
3. EGCG daily with letrozole 5mg for 5 days.

The purpose of studying EGCG in combination with clomiphene citrate or letrozole is to assess the safety of using them together prior to the initiation of the FRIEND study. It is expected that EGCG will decrease fibroid size and decrease humoral activity leading to improved quality of endometrium for implantation. Clomiphene citrate and letrozole are being used for ovulation stimulation as treatment for unexplained infertility. In view of the possibility of interaction and change in toxicity when both are used together for FRIEND study, it was suggested by our pharmacology reviewer to include EGCG with the addition of clomiphene citrate and letrozole for the safety study.

The initial screening visit will include EGCG levels, liver function, folate and estrogen levels. A genetics sample collection, urine pregnancy test and pelvic ultrasound will also be performed after informed consent. Patient will be given the EGCG (Green Tea extract) to start after the screening visit. Patients will be counseled on dietary restrictions while on EGCG.

Visit 1 will occur on menstrual cycle day  $3 \pm 2$  days. EGCG levels over 8 hours, liver function, and urine pregnancy testing will occur at this visit. Patients will be assigned into their groups and provided with their respective treatments at this visit.

Patient will return between days 8-10 of the cycle for Visit 2. EGCG levels over 8 hours, liver function, estrogen, and urine pregnancy testing will occur at this visit.

The patient will return for Visit 3 between days 14-16 for a pelvic ultrasound evaluation of endometrial thickness and ovarian characteristics.

The final study visit (Visit 4) will be approximately 4 weeks after initiation of the study treatment and will involve EGCG levels, liver function, folate, and urine pregnancy test and pill counts.

The 4 lab panels (screening, Visits 1, 2, and 4) will include EGCG and metabolite analyses, liver panel (AST, ALT, total bilirubin, ALP) and estrogen levels, and a urine pregnancy test. The EGCG analyses at visits 1 and 2 will include testing over 8 hours.

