#### 4.3.3 Study Summary

Recruitment and Prescreening: see Section 5 descriptions following.

Screening visit (anytime in cycle 1):

1. Obtain informed, signed consent.
2. Complete medical/gynecological/menstrual history and physical exam of female study participant.
  - Vital signs, height, weight, hip and abdominal circumference, BMI
  - Pap smear if necessary per current ACOG time-frame guidelines
  - Standard pelvic and breast exam conducted by physician or within past 12 months
3. Perform radiological exams.
  - Pelvic ultrasound measuring uterine and ovarian characteristics or within past 3 months
4. Laboratory tests: EGCG and metabolites, liver function, folate, estrogen levels, genetics sample collection and urine pregnancy test.
5. Dispense Green Tea extract and educate on dietary restrictions while taking Green Tea extract and with the importance of taking food. All patients to start Green Tea extract at this visit.
6. Contraception education. Patients will be counseled to use non-hormonal double-barrier method: a male/female condom plus spermicidal agents, cervical cap, diaphragm or sponge.
7. Concomitant medication collection.

Visit 1 (Day 1-5):

Patient will be seen on menstrual cycle day  $3 \pm 2$  days for clomiphene citrate/letrozole initiation visit

1. Vital signs and weight.
2. Laboratory tests: EGCG levels over 8 hours (0.5,1,2,4,6,8), liver function, folate, estrogen level, and urine pregnancy testing.
3. Concomitant medication collection and pill counts of EGCG.
4. Randomization and dispensation of clomiphene citrate/letrozole.
5. Contraception education. Patients will be counseled to use non-hormonal double-barrier method: a male/female condom plus spermicidal agents, cervical cap, diaphragm or sponge.

Visit 2 (day 8-10):

Patient will return several days after final clomiphene citrate/letrozole administration

1. Vital signs and weight.
2. Laboratory tests: EGCG levels over 8 hours (0.5,1,2,4,6,8), liver function, folate, estrogen level and urine pregnancy testing.

3. Concomitant medication collection and pill counts of EGCG and clomiphene citrate or letrozole as appropriate.
4. Contraception education. Patients will be counseled to use non-hormonal double-barrier method: a male/female condom plus spermicidal agents, cervical cap, diaphragm or sponge.

Visit 3 (day 14-16):

1. Pelvic ultrasound via a transvaginal probe or transabdominal transducer evaluation of endometrial thickness and ovarian characteristics.

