## 5.9 Schedule of Evaluations

Study procedure	Cycle 1					Cycle 2				
	Screening	Visit 1 (Day 1 -5)	Visit 2 (Day 8 -10)	Visit 3 (Day 14-16)	Visit 4 (Day 30 - 35)	Visit 5 (Day 36-42)	Visit 6 (Day 43-49)	Visit 7 (Day 50-56)	Visit 8 (Day 57-63)	Visit 9 (Day 64-70)
Informed consent	X									
Inclusion/exclusion criteria	X									
Demographic information	X									
Medical history	X									
Concomitant medications	X	X	X						X	
Gynecological history	X									
Menstrual history	X									
Vital signs and weight	X	X	X						X	
Height	X									
Hip and abdominal circumference	X									X
Physical examination	X									
Pap smear	X*									
Pelvic and breast exam	X**									
Genetics sample, laboratory test	X									
Pelvic ultrasound	X †						X			
EGCG levels and metabolites, laboratory test	X	X	X						X	
Liver function, laboratory test	X	X	X						X	
Folate, laboratory test	X								X	
Estrogen levels, laboratory test	X	X	X							X
Contraceptive counseling	X	X	X							
Dispense EGCG	X									
Pill counts of EGCG		X	X						X	
Randomization and dispensation of clomiphene citrate or letrozole			X							

Pill counts of clomiphene citrate and letrozole			X		
Urine pregnancy test	X	X	X		X

\*If necessary per ACOG guidelines

\*\*if not done within past 12 months

† if not done within past 3 months

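### Folate is drawn at four visits in 4.3.3 but at two in 2.4 and 5.9, so half of all folate samples, and two thirds of those on EGCG, depend on the section followed

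*Combined protocol and SAP*

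**What the plan says.** All three places are in the current text of the combined protocol and SAP.

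- **Section 4.3.3 (Study Summary)** lists folate at screening, Visit 1, Visit 2 and Visit 4. The Visit 1 entry reads "EGCG levels over 8 hours (0.5,1,2,4,6,8), liver function, folate, estrogen level, and urine pregnancy testing"; Visit 2 has the same tests.
- **Section 2.4 (Treatment)** gives folate at screening ("The initial screening visit will include EGCG levels, liver function, folate and estrogen levels") and at Visit 4 ("will involve EGCG levels, liver function, folate, and urine pregnancy test and pill counts"). The lists for the two visits in between omit it: "EGCG levels over 8 hours, liver function, and urine pregnancy testing will occur at this visit" for Visit 1 and "EGCG levels over 8 hours, liver function, estrogen, and urine pregnancy testing will occur at this visit" for Visit 2. The summary sentence begins "The 4 lab panels (screening, Visits 1, 2, and 4) will include EGCG and metabolite analyses, liver panel" and goes on to estrogen and a pregnancy test, without folate.
- **Section 5.9 (Schedule of Evaluations)** has a row "Folate, laboratory test" with two marks. The EGCG, liver and estrogen rows have four each.

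Section 2.1 asks whether women with MTHFR polymorphisms are at greater risk of folate depletion on green tea extract. Section 2.6 makes the folate comparison by MTHFR group a secondary outcome. Sections 2.7 and 6.4 plan an unadjusted ANOVA and a linear regression. They name no visit, no change from screening, and no covariates.

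**The concern.** A site or data manager working from 2.4 or 5.9 would collect half the folate samples that 4.3.3 orders. EGCG is started at screening, so the screening folate is the only pre-treatment value and every later one is on EGCG. Under 2.4 and 5.9 there is just one of these per woman. A woman who misses the final visit then contributes nothing to the depletion question. In two of the three arms, the single value also comes after clomiphene or letrozole.

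One route to such loss is in the protocol itself: 4.3.6 takes women with a liver test at three times the upper limit out of the study. Losses of that kind could be related to EGCG exposure rather than random.

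The analysis text does not settle the matter. Because it names no visit, it fits either schedule. It also compares folate levels between genotype groups, whereas depletion is a fall from each woman's own starting value.

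**Working it through.** The plan states no number of folate samples, so there is no figure to reproduce. The check is a comparison of the sections and a count.

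**Step 1. The sections side by side**

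| Visit | 4.3.3 | 2.4 visit lists | 2.4 four-panel sentence | 5.9 folate row |
|---|---|---|---|---|
| Screening | yes | yes | not named | marked |
| Visit 1 | yes | not listed | not named | no mark |
| Visit 2 | yes | not listed | not named | no mark |
| Visit 4 | yes | yes | not named | one late mark, visit uncertain |

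In the text as extracted, the second folate mark in 5.9 falls under the column for Visit 8, as do the last EGCG and liver marks. The table heads Visits 5 to 9, which no text describes, so column positions cannot be trusted. The number of marks, two against four, does not depend on them.

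**Step 2. Samples at stake**

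Input: "The population will consist of 36 women ages" (2.2), so n = 36.

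- All samples under 4.3.3: 36 × 4 = 144. Under 2.4 and 5.9: 36 × 2 = 72. Difference 72, and 72/144 = 50%.
- On-EGCG samples (all after screening) under 4.3.3: 36 × 3 = 108. Under 2.4 and 5.9: 36 × 1 = 36. Difference 72, and 72/108 = 67%.

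**Step 3. Women with no on-EGCG folate**

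Let d be the share who miss the final visit. The documents give no value for this trial, so 5-20% is an assumption. For orientation only, the EGCG trial described in 3.3 had 33 of 39 women complete, and 6/39 = 15.4%.

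- Under 2.4 and 5.9 the expected number is 36 × d.
- Under 4.3.3, if visits were missed independently, it is 36 × d³.

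| d | 2.4 and 5.9: 36 × d | 4.3.3: 36 × d³ |
|---|---|---|
| 5% | 1.8 | 0.005 |
| 10% | 3.6 | 0.04 |
| 15.4% | 5.5 | 0.13 |
| 20% | 7.2 | 0.29 |

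Independence is generous, because a woman who drops out misses all later visits. The conclusion for 4.3.3 does not rest on it, though: 2.4 and 4.3.3 both assign treatment at Visit 1, so a randomised woman has attended at least one visit at which 4.3.3 draws folate on EGCG.

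**The case against.** The strongest reply is that this is a drafting inconsistency with limited consequences. Several parts of it stand.

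- **Nothing forbids the extra draws.** Section 2.4 omits folate at Visits 1 and 2 but does not exclude it. Drawing folate at all four visits would satisfy every positive statement; only the blank cells in 5.9 point the other way. This is right, and it makes reconciliation easy, but it does not tell a site what to do.
- **Sites would not necessarily differ.** A reader might infer that the four sites would each choose a section, leaving Visit 1 and 2 folate missing by site. The documents do not support that. Data go into one system built by the coordinating centre (6.1), and that centre trains and initiates sites (7.6). One reading applied everywhere is at least as likely. If it were that of 2.4 and 5.9, one on-EGCG value per woman would still be the result.
- **Stored blood may help.** Section 4.3.3 stores a tube from each visit for future analyses. Tube type and suitability for folate are not stated, so later assay may or may not be possible.
- **The stated outcome needs only two values.** No folate time course or comparison by treatment arm is planned, and the study calls itself underpowered for formal inference. One screening and one final value can serve the stated comparison. The Visit 1 and 2 samples are therefore supportive and a safeguard against loss.
- **The cited 15.4% comes from a different setting.** It is from a 4-month trial in symptomatic women, whereas the final visit here is about 4 weeks after treatment starts. Hence the range.
- **Two of the three sections agree on two draws.** Nothing shows that 4.3.3 is the intended version. The preference for it rests on the objective in 2.1 and on low cost.

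**Conclusion.** The inconsistency is real and should be corrected. The sections disagree on 72 of 144 folate samples, and on 72 of 108 taken on EGCG. Under 2.4 and 5.9 the depletion question rests on one on-EGCG value per woman, and about 2 to 7 of 36 women would have none if 5-20% miss the final visit. That range is assumed. The sample counts are not; they follow from the text and the 36 women.

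Three further readings go beyond the documents:

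- One might claim a specific gain in precision from averaging three on-EGCG values. That needs correlations between visits that the documents do not give. Screening can fall anywhere in the first cycle, so EGCG exposure at Visit 1 varies and may be short, and an average would estimate something different from the final value.
- One might say that 5.9 places the second folate draw at Visit 4. The extracted table shows only that there are two marks.
- One might see a matching conflict over estrogen, because the 2.4 lists for Visits 1 and 4 omit it. The four-panel sentence in 2.4, together with 4.3.3 and the four marks in 5.9, settles estrogen at four draws. Only the wording of the lists needs repair.

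The point concerns a secondary outcome and leaves the pharmacokinetic comparison untouched. It is worth fixing because the change is cheap and a sample that is not taken may not be recoverable.

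**What to change.** 1. Reconcile 2.4 and 5.9 with 4.3.3, so that folate is drawn at screening and Visits 1, 2 and 4. Name folate in the four-panel sentence of 2.4, and check that the final mark in 5.9 stands under the intended visit. Table 1 in 5.8, as extracted, lists no folate test; confirm that the source table does.
2. List estrogen in the 2.4 entries for Visits 1 and 4, to match its own four-panel sentence.
3. In 2.7 and 6.4, name the folate analysis: final-visit folate compared among MTHFR groups, with screening folate as a covariate, because the question is depletion on EGCG. The planned linear regression can carry this.
4. Report Visit 1 and 2 folate as supportive data. Add a sensitivity analysis with a repeated-measures model of all on-EGCG values, with visit in the model and screening folate as covariate, so that women without a final visit are kept.

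The cost is wording in these sections and at most 36 × 2 = 72 folate assays beyond 2.4, with none beyond 4.3.3. No extra venepuncture is needed, because blood is already drawn over 8 hours at Visits 1 and 2.

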## **2.5 Primary Outcome Parameter**

The primary outcome parameter will be differences in pharmacokinetic parameters of EGCG and the major metabolites between the 3 groups.

## **2.6 Secondary Outcome Parameters**

The secondary outcome parameters will include:

- Changes in liver function between the 3 groups.
- Changes in estrogen levels (E2) between the 3 groups.
- Changes in endometrial thickness and ovarian characteristics between the 3 groups.
- Change in the pharmacokinetic parameters of EGCG and metabolites within each group.
- Difference in serum folate levels among wildtype MTHFR, MTHFR (C677T), and MTHFR (A1298C) patients.

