## **2.7 Statistical Analysis**

Since the number of patients for this study is minimal and multiple factors are of concern, descriptive statistics will be used, and the study is expected to be under powered to perform any formal statistical inference. The number, mean, standard deviation, median, interquartile range of the level of the pharmacokinetic parameters of EGCG and 2 of the major metabolites at different time points and the difference from screening to Visit 1, Visit 2 or Visit 4, and the changes in liver function, estrogen levels, endometrial thickness, and follicular measurements will be presented for the three treatment groups, and then stratified by age group and/or the presence or absence of uterine fibroid. For comparison, a two-way ANOVA will be used to compare the effects of the three treatments and the presence of fibroids on the above outcome parameters. With a sample size of 36 patients for the three treatment groups, which includes 18 subjects with uterine fibroids and 18 without uterine fibroids, with an alpha of 0.05, the power of the study would be 0.44 and 0.85 for a medium (0.25) or large (0.4) effect size, respectively. There are insufficient preliminary data

in the literature to support or not support the reasonableness of these effect sizes. For the comparison of serum folate levels among wildtype MTHFR, MTHFR (C677T), and MTHFR (A1298C) patients, ANOVA (unadjusted) and multivariate linear regression will be used.

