**Figure 1. Flowchart**

## 4 Objectives

### 4.1 Primary Aim

Our goal is to assess the pharmacokinetics and hepatic safety of EGCG in women with and without uterine fibroids.

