### 5.2 Rationale for Design

The pharmacokinetics and hepatic safety of EGCG with clomiphene citrate and letrozole are unknown. A 3-arm study will be conducted in women with and without fibroids to allow comparisons between these groups. The results of this study will be used to confirm hepatic safety for the larger multi-center FRIEND study. The pharmacokinetics and hepatic safety of EGCG with clomiphene citrate and letrozole are unknown. A 3-arm study will be conducted in women with and without fibroids to allow comparisons between these groups. The results of this study will be used to confirm hepatic safety for the larger multi-center FRIEND study.

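### The only formal liver comparison is among women who all take EGCG, so it cannot detect a liver effect of EGCG common to the arms, which is what the stated objective asks about

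*Combined protocol and SAP*

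**What the plan says.** **Objective and use.** Section 2.1 sets the objective as the pharmacokinetics and hepatic safety of EGCG. Section 4.1 repeats it as the only aim: "Our goal is to assess the pharmacokinetics and hepatic safety of EGCG in women with and without uterine fibroids". Section 4.2 gives no secondary aim. Section 5.2 adds: "The results of this study will be used to confirm hepatic safety for the larger multi-center FRIEND study".

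**Exposure.** All three arms receive the same daily EGCG (4.3.2, 5.5), and no arm is without it. At the screening visit the laboratory panel is listed before dispensing, and then: "All patients to start Green Tea extract at this visit" (4.3.3). Randomization and the added drug come at Visit 1.

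**Liver outcome.** Sections 2.6 and 6.3 define it as "Changes in liver function between the 3 groups". The same lists include a within-group change, but only for the pharmacokinetic parameters.

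**Analysis.** Sections 2.7 and 6.4 begin by calling the study descriptive and underpowered. They plan the number, mean, SD, median and interquartile range of the changes in liver function by arm, then by age group and/or fibroid status. The inferential step is "a two-way ANOVA will be used to compare the effects of the three treatments and the presence of fibroids on the above outcome parameters".

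**Combination purpose.** Section 2.4 states a second purpose: "The purpose of studying EGCG in combination with clomiphene citrate or letrozole is to assess the safety of using them together".

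**Liver rules.** Section 4.3.6 takes a woman off study at 3 times the upper limit of normal. It ends the trial if three or more participants, all arms together, meet its definitions of active liver disease.

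**The concern.** The comparator in the formal test does not match the question in the objective. The arms differ only in whether clomiphene or letrozole is added, so comparing them isolates the added drug. The comparator for EGCG is each woman's own liver panel before EGCG. That panel is collected, but it is not the basis of any named liver outcome.

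At stake is the use of the result. The larger trial is described in 3.1 as EGCG against placebo, and this study is meant to support its hepatic safety. The number it most needs is the liver change on EGCG relative to before EGCG. No pooled estimate or interval is planned for that change, and there is no statement of what would count as confirmation.

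**Working it through.** **Inputs.** N = 36 in three equal arms, so 12 per arm; 18 women with and 18 without fibroids (2.2, 4.3.2); alpha 0.05 (2.7). Balance gives 36 / 6 = 6 women per arm-by-fibroid cell (assumed, with all 36 evaluable). The documents give no SD for liver change, so effects are in units of the SD of the within-woman change.

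**Step 1: the plan's own power figure.** Sections 2.7 and 6.4 give power 0.44 and 0.85 for effect sizes f = 0.25 and 0.40. With the noncentral F and λ = f²N, λ = 0.0625 × 36 = 2.25 and 0.16 × 36 = 5.76. This gives:
- treatment factor (2, 30 df): 0.23 and 0.52;
- fibroid factor (1, 30 df): 0.31 and 0.64.

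The stated figures are not reproduced at N = 36; N = 72 (2, 66 df) gives 0.443 and 0.853. That mismatch is a separate matter. It does not decide this point, because f measures differences between groups, and an effect common to all groups has f = 0 at any N.

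**Step 2: a common effect cancels.** Write a woman's change in a liver test as Y = μ + arm + fibroid + interaction + error, and add a constant δ to every Y.
- Treatment sum of squares: 12 Σ(arm mean − grand mean)². Both means rise by δ, so the difference is unchanged.
- Fibroid sum of squares: 18 Σ(fibroid-group mean − grand mean)². Unchanged for the same reason, since both fibroid groups take EGCG.
- Error sum of squares: deviations from cell means. Unchanged.

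Every F statistic is therefore exactly the same with or without δ. The effect sits in μ, which the plan does not test. The same holds with unequal cells, because the model contains an intercept.

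As a check, 20,000 balanced trials were simulated at each common shift of 0.25, 0.5, 0.8, 1 and 2 SD. The treatment test rejected in 0.048 to 0.051 of trials and the fibroid test in 0.049 to 0.052, which is alpha.

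**Step 3: what the same data can show.** For the mean within-woman change, the 95% half-width is t(0.975, n − 1)/√n:
- pooled, n = 36: 2.030 / 6 = 0.34 SD;
- one arm, n = 12: 2.201 / 3.464 = 0.64 SD.

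Power of a two-sided one-sample t test, noncentrality shift × √n:

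| Common shift (SD) | Planned treatment F test | Pooled change, n = 36 | One arm, n = 12 |
|---|---|---|---|
| 0.25 | 0.05 | 0.31 | 0.12 |
| 0.5 | 0.05 | 0.83 | 0.35 |
| 0.8 | 0.05 | 0.997 | 0.71 |

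The shifts are illustrative; the first column does not depend on them.

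**Step 4: threshold events.** With no events in n women, the exact one-sided 95% upper bound is 1 − 0.05^(1/n): 8.0% for 0/36 and 22.1% for 0/12. Section 4.4.2 describes transaminase elevations as rare, below 5%. A count of zero in this trial could not exclude a rate of that size.

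**The case against.** The case for the plan has four parts.

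1. **Change from screening is already described.** Sections 2.7 and 6.4 put description first, and the screening panel precedes EGCG. A common rise would appear as three non-zero mean changes, and an interval could be computed from each arm's n, mean and SD. This stands. A reader might infer that the plan makes no use of the pre-EGCG baseline, or that a common effect would be invisible. The documents support neither. What is missing is a named pooled estimate, an interval and a criterion. In the two combination arms, change after Visit 1 also mixes EGCG with the added drug.

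2. **Absolute liver rules apply.** Those in 4.3.6 need no control arm and pool over arms, so they respond to toxicity shared by the arms. This also stands. They protect participants, but do not estimate an effect or its uncertainty.

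3. **The between-arm contrast has a proper purpose.** Section 2.4 asks about the combinations, and the rationale in 3.1 and 5.2 places the confirmation of hepatic safety directly after saying that EGCG with clomiphene or letrozole is unstudied. For that question the EGCG-alone arm is the right control. Agreed: the contrast should stay. It does not answer the objective as worded in 2.1 and 4.1. The fibroid factor can show that a liver change differs by fibroid status, but not a change common to both groups.

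4. **The plan disclaims formal inference.** A reader might infer that a non-significant ANOVA will be reported as proof of safety. No section says so. The risk is only that the plan supplies this test, with alpha and power, and nothing else inferential for the liver.

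**Conclusion.** The concern holds in a limited form. The formal liver comparison addresses the addition of clomiphene or letrozole. It carries no information on a liver effect of EGCG common to the arms, at any sample size. That result is algebraic and rests only on all arms taking the same EGCG. The within-woman changes that do bear on the objective are planned only as descriptive summaries by arm.

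The gain from the change is one of precision and explicitness: a half-width of about 0.34 SD pooled against 0.64 SD per arm, assuming 36 evaluable women, roughly normal changes and a similar SD across arms.

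The within-woman estimate has limits of its own:
- With no EGCG-free control, time trends and regression to the mean remain.
- Screening may fall at any time in cycle 1 while Visit 1 is tied to cycle days 1 to 5, so EGCG exposure before Visit 1 varies between women.
- Section 4.4.2 places most hepatotoxicity at roughly 3 to 4 months, beyond the up to 2 months of dosing here, so no analysis of this trial can speak to later onset.

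**What to change.** **Outcomes (2.6, 6.3).** Add within-woman change in liver function from the pre-EGCG screening panel as the outcome for the EGCG objective. Keep the between-group comparison and label it as the question of adding clomiphene or letrozole.

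**Analysis (2.7, 6.4).** For ALT, AST, ALP and total bilirubin, report mean change with 95% confidence intervals for:
- (a) screening to Visit 1, pooled over all women: EGCG before any added drug;
- (b) screening to Visits 2 and 4 in the EGCG-alone arm;
- (c) screening to Visits 2 and 4 averaged over the arms, labelled EGCG with or without the added drug.

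Also report, overall and by arm, the number and proportion of women crossing the protocol's existing liver thresholds, with exact intervals. Include repeat tests, so that a woman taken off study under 4.3.6 still counts.

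**Interpretation.** State that a non-significant between-arm ANOVA is not evidence on the hepatic safety of EGCG, and list the three limitations given in the verdict.

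**Cost.** Wording in four sections and one extra table. No new visits, samples or participants are needed.
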